4.3.3. Rationale for Trial Design

This Phase 2 trial is designed to evaluate the efficacy and safety of a single 600 mg SC dose of rademikibart as adjunct therapy to standard therapy in adult participants with COPD characterized by an eosinophilic phenotype (peripheral blood eosinophil counts of ≥ 300 cells/ μ L at Screening Visit 1b or as part of the assessment of the index acute COPD exacerbation within 72 hours prior to Screening) who require urgent healthcare treatment for an acute COPD exacerbation. A randomized, placebo-controlled trial design where the effect of the investigational product (IP) is assessed on top of the standard therapy is considered to be the most appropriate design to explore the efficacy and safety of a novel biologic therapy in COPD exacerbation. Similar trial designs and endpoints have been employed for recent trials with other biologics and small molecule drugs in acute exacerbation (Fahy et al. 2021; Ramakrishnan, Russell, et al. 2024). In addition, this trial intends to assess the PK profile of rademikibart in the trial population.

The primary endpoint of treatment failure rate has been widely used in interventional clinical trials in COPD exacerbations (de Jong et al. 2007; Ramakrishnan, Jeffers, et al. 2024; Ramakrishnan, Russell, et al. 2024). The proposed primary endpoint would support the investigation of the hypothesis that rademikibart reduces the treatment failure rate for index acute COPD exacerbations during the vulnerable period in the targeted trial population: those experiencing an acute COPD exacerbation with high eosinophil counts and a history of exacerbations. This trial is also designed to evaluate the efficacy of rademikibart compared to placebo as an adjunct to standard therapy on subsequent COPD exacerbations in the targeted trial population.

4.3.4. Rationale for Comparator

Placebo has been chosen as the control group as there is no biologic approved for the treatment of acute exacerbations of COPD. There is no anticipated risk for participants randomized to the placebo group, as all participants will receive the standard therapy for the acute COPD exacerbation, including oral/systemic corticosteroids (prednisone 40 mg/day or equivalent), antibiotics, and/or other medical interventions at the discretion of the Investigator or a medically qualified designee. In addition, participants are instructed to continue their regular COPD maintenance treatments throughout the trial.

4.3.5. Rationale for Trial Population

This trial targets participants with COPD characterized by an eosinophilic phenotype who are experiencing an acute exacerbation and are at high risk for future exacerbations. This represents a population with significant unmet medical need in this disease who will potentially benefit from this trial.

The clinical trial population includes adult participants with COPD with an eosinophilic phenotype, with an appropriate age range of 40 to 80 years, inclusive, and history of a COPD

exacerbation requiring the use of systemic corticosteroids in the previous year. Participants in this trial must experience an acute COPD exacerbation with a blood eosinophil counts of ≥ 300 cells/ μL and required systemic corticosteroids as standard of care (SoC) treatment in the urgent healthcare setting for the current acute COPD exacerbation.

Patients with eosinophilic COPD exacerbations, characterized by blood eosinophil counts of ≥ 300 cells/ μL , have a higher frequency of hospital readmissions and new exacerbations within one year (Hasegawa and Camargo 2016). Dupilumab, as a maintenance therapy, has shown robust and consistent clinical efficacy in patients with COPD exhibiting evidence of type 2 inflammation, guided by blood eosinophil counts of ≥ 300 cells/ μL at Screening. This raises the possibility that rademikibart could be an effective therapy in the acute setting for patients with an eosinophilic COPD exacerbation characterized by blood eosinophil counts of ≥ 300 cells/ μL .

4.4. Compliance

The trial site is required to adhere to all applicable laws, regulations, and guidelines including, but not limited to, the US Code of Federal Regulations (CFR), International Council for Harmonisation (ICH), Health Insurance Portability and Accountability Act (HIPAA) of 1996, Good Radiation Practice, as well as any applicable local and federal regulations.

4.4.1. Regulatory Safety Reporting Requirements

The Investigator must promptly report to the Sponsor all serious adverse events (SAEs), unanticipated adverse device effects (UADEs), adverse events of special interest (AESIs), and suspected drug-induced liver injury (DILI) events as defined in accordance with the procedures detailed in Section 11.7. The Sponsor has a legal responsibility to notify, as appropriate, both the local regulatory authority and other regulatory agencies about the safety of a product under clinical investigation. Prompt notification by the Investigator of urgent safety reports as described in Section 11.7 to meet legal obligations and ethical responsibilities regarding the safety of other participants is required.

Investigator letters are prepared according to Sponsor policy and are forwarded to the Investigators as necessary. An Investigator letter is prepared for any suspected adverse reaction that is attributable to IP, that is both serious and unexpected. The purpose of the Investigator letter is to fulfill specific regulatory and Good Clinical Practice (GCP) requirements regarding the product under investigation.

The Investigator, or responsible person according to local requirements, must comply with requirements related to the reporting of SAEs to the Institutional Review Board (IRB)/ Independent Ethics Committee (IEC).

The Sponsor is responsible for informing IRBs/IECs, Investigators, and regulatory authorities of findings that could adversely affect the safety of participants or affect the conduct of the trial. Events will be reported to regulatory authorities in accordance with expedited and periodic reporting requirements.

4.4.2. Unanticipated Problems

Unanticipated problems are incidents, experiences, or outcomes that **meet all of the following criteria**:

- Unexpected in terms of nature, severity, or frequency given (a) the research procedures that are described in the protocol-related documents, such as the research protocol and informed consent document approved by the IRB/IEC and (b) the characteristics of the participant population being studied.
- Related or possibly related to participation in the research (“possibly related” means there is a reasonable possibility that the incident, experience, or outcome may have been caused by the procedures involved in the research).
- Suggest that the research places participants or others at a greater risk of harm (including physical, psychological, economic, or social harm) than was previously known or recognized.

Only a small subset of adverse events (AEs) occurring in trial participants will meet these 3 criteria for an unanticipated problem. The following single occurrences of AEs should be considered as unanticipated problems that must be reported to the IRB/IEC:

- An unexpected SAE that is uncommon and strongly associated with drug exposure (such as angioedema, agranulocytosis, hepatic injury, or Stevens-Johnson syndrome).
- An unexpected SAE that is not commonly associated with drug exposure, but uncommon in the trial population (eg, tendon rupture, progressive multifocal leukoencephalopathy).
- An AE that is described or addressed in the IB, protocol, or ICF documents, but occurs at a specificity or severity that is inconsistent with prior observations. For example, if transaminase elevation is listed in the investigator’s brochure and hepatic necrosis is observed in trial participants.

Refer to Section [11.3.2](#) for definition of an SAE and Section [11.3.6](#) for the definition of an unexpected AE.

Furthermore, there are other types of incidents, experiences, and outcomes that occur during the conduct of clinical trials that represent unanticipated problems but are not considered AEs. For example, some unanticipated problems involve social or economic harm instead of the physical or psychological harm associated with AEs (eg, theft of a trial laptop that included individually identifiable sensitive information about a trial participant). In other cases, unanticipated problems place participants or others at increased *risk* of harm, but no harm occurs (eg, a dosing error increased the risk of toxic manifestations of the IP, but the participant experienced no AE).

If the Investigator determines that an event meets the definition of an unanticipated problem, he/she must notify the Sponsor or designee **within 24 hours** of the Investigator becoming aware of the problem.

The following information will be included with unanticipated problem reporting:

- Protocol identifying information: protocol title, protocol number, and Investigator’s name.
- A detailed description of the event, incident, experience, or outcome.
- An explanation of the basis for determining that the event, incident, experience, or outcome represents an unanticipated problem.

It is the Investigator's responsibility to report unanticipated problems to their IRB/IEC, as required by local regulations.

For this multicenter trial, the Investigator may rely on the Sponsor's assessment of unanticipated problems that are based on aggregate analysis of AEs received from multiple clinical trial sites or from other information and provide to the IRB a report of the unanticipated problem prepared by the Sponsor. These include the following:

- Multiple occurrences of an AE that, based on an aggregate analysis, are determined to be an unanticipated problem.
- A small number of occurrences of an unexpected SAE that are not commonly associated with drug exposure, but uncommon in the trial population (eg, tendon rupture, progressive multifocal leukoencephalopathy)
- An SAE that is described or addressed in the IB, protocol, or ICF documents, but for which the rate of occurrence in the trial represents a clinically significant increase in the expected rate of occurrence (ordinarily, reporting would only be triggered if there was a credible baseline rate for comparison).
- Any other AE or safety finding (eg, based on animal or epidemiologic data) that would cause the Sponsor to modify the IB, trial protocol, or ICF documents, or would prompt other action by the IRB/IEC to ensure the protection of human subjects.

4.4.3. Protocol Deviations

A protocol deviation is any modification to protocol-specified procedures, whether intentional or not, that occur without prior IRB/IEC approval and submission to regulatory authority(ies) of the protocol amendment implementing the modification. The Investigator will not implement any protocol modification without prior approval of the IRB/IEC and agreement by the Sponsor except where necessary to eliminate an apparent immediate hazard to trial participants.

Protocol deviations fall into 2 categories:

- Important Protocol Deviations.
- Other Protocol Deviations.

Important Protocol Deviations are deviations that might significantly affect the completeness, accuracy, and/or reliability of the trial data or that might significantly affect a participant's rights, safety, or well-being. Some examples include:

- Failure to conduct trial procedures designed to assess participant safety or failure to adequately monitor participants.
- Administration of concomitant treatment prohibited by the protocol that may increase risks to participants and/or impact interpretation of safety and efficacy.
- Failure to obtain informed consent or meet other applicable requirements for the protection of human participants.
- Failure to protect a participant's identifiable private protected health information.

- Enrollment of a participant in violation of key eligibility criteria designed to ensure a specific participant population.
- Failure to administer the IP according to specifications in the protocol, administration of the wrong treatment or incorrect dose to participants.
- Failure to collect data to evaluate important trial endpoints (eg, primary or secondary endpoints).
- Premature unblinding of a participant's treatment allocation for reasons other than those specified in the protocol.
- Failure to withdraw IP administration from participants who meet withdrawal criteria.

Other Protocol Deviations are those that do not meet the definition of an Important Protocol Deviation. Some examples of all Other Protocol Deviations include small deviations from protocol-specified visit windows; a signed consent missing a participant's initials on a page; or failure to perform a trial procedure not relevant for safety monitoring or not related to an important trial efficacy endpoint (eg, primary or secondary endpoints).

For any protocol deviation, the Investigator will document it in the participant's source documents, indicating if any are an Important Protocol Deviation, and notify the Sponsor or designee. The Investigator will discuss the Important Protocol Deviation with the Sponsor's Medical Monitor or designee to reach an agreement on whether the participant should be withdrawn from the trial. The Investigator will notify the IRB/IEC of Important Protocol Deviations, as required by IRB/IEC guidelines and site requirements. The Sponsor is responsible for notifying the regulatory authorities, if required.

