6.5.1. Safety Criteria for Adjustment or Stopping Doses

Dosing for any individual participant will be stopped if the participant experiences a drug-related SAE or a drug-related significant nonserious AE which, in the opinion of the Investigator, physician, or Sponsor's medical representative, warrants discontinuation of the trial for that participant's well-being.

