7.5. Discontinuation of IP

If a participant is discontinued from IP, the participant will be asked to continue attending trial visits to the EOT Visit (Week 8).

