7.5.1. Criteria for Permanent Discontinuation of IP

Participants should be discontinued from IP in the event of:

1. The participant withdraws his/her consent to participate in the trial.
2. Anaphylactic reaction or other severe hypersensitivity reaction attributed to IP administration.
3. AE, laboratory abnormality, or inter-current illness which, in the opinion of the Investigator, indicates that continued treatment and/or participation in the trial is not in the best interest of the participant
4. Evidence of pregnancy.
5. Participant is significantly non-compliant with trial procedures which would put the participant at risk for continued participation in the trial in consultation with the Sponsor Medical Monitor or designee.
6. Important protocol deviation or requirement for medication or procedure prohibited by the protocol.
7. Severe laboratory abnormalities ([Appendix C](#)):
 - a. AST and/or ALT $\geq 3 \times$ ULN in combination with total bilirubin $\geq 2 \times$ ULN and no other explanation other than IP can be determined.
 - b. Confirmed AST and/or ALT $> 5 \times$ ULN (for more than 2 weeks).

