11.6. Recording Adverse Events

All AEs regardless of causality will be recorded in the EDC from the time the participant signs the ICF through the participant's last visit or 28 days post last dose, whichever is longer. AEs that occur after signing of the ICF but prior to IP administration should be recorded on the Medical and Surgical History eCRF. AEs reported during this time that are serious should also be reported as an SAE (Section 11.7.1). Any clinically significant findings as determined by the Investigator, or changes from the time of signing the ICF, should be recorded on the AE or Medical History eCRF, as applicable.

For participants who received IP, if an Investigator becomes aware of an SAE that occurs after the participant's trial participation ends and the Investigator considers the event to be possibly

related to the IP, the Investigator should report the SAE to the Sponsor as described in Section 11.7.1.

11.7. Safety Reporting to the Sponsor of Serious Adverse Events and Other Safety Reports

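### The protocol does not separate stopping the investigational product from leaving the trial, so a deviation or adverse event after the only dose can end follow-up

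*Protocol*

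**What the plan says.** All IP is given on Day 0 (Protocol 6.3), and Section 7.5.2 confirms that this is a single-dose trial. The protocol then treats the same events in two ways.

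- **Follow-up continues.** Under Section 7.5, after discontinuation of IP, "the participant will be asked to continue attending trial visits to the EOT Visit (Week 8". Section 7.5.1 item 6 lists this as a ground for discontinuing IP: "Important protocol deviation or requirement for medication or procedure prohibited by the protocol". Section 7.6 asks the Investigator to try to retain everyone randomized.
- **Follow-up may end.** Under Section 4.4.3, an important deviation is discussed between the Investigator and the Medical Monitor "to reach an agreement on whether the participant should be withdrawn from the trial". Examples given there include "Failure to administer the IP according to specifications in the protocol, administration of the wrong treatment or incorrect dose to participants". Section 6.5.1, a dose-stopping rule, refers to a drug-related event that "warrants discontinuation of the trial for that participant". Section 7.5.1 item 3, in the list of grounds for stopping IP, covers an event that "indicates that continued treatment and/or participation in the trial is not in the best interest of the participant".

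A randomized participant who leaves early has one End of Trial visit as soon as possible (7.6). Adverse events are recorded through the "last visit or 28 days post last dose, whichever is longer" (11.6). The primary analysis uses observed data in the Full Analysis Set (13.4.5).

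**The concern.** In a repeated-dose trial, the decision to stop treatment and the decision to stop observing can be confused at some cost. Here nothing remains to be stopped once the dose is in. The only effect of trial withdrawal is to end data collection, and the protocol opens that route for the events named in 4.4.3 and 6.5.1. Two sites could handle the same deviation in opposite ways, and each could cite the protocol.

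Two things are at stake. The first is follow-up after a wrong dose, a prohibited therapy or a drug-related event, where later safety data are most wanted. The second is the primary endpoint: a discretionary decision taken after randomization can determine whether a participant contributes an outcome. Because Section 6.5.1 acts on drug-related events, such decisions could plausibly differ by arm.

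**Working it through.** **1. The same trigger under each section, for a participant already dosed**

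| Trigger | Route that keeps follow-up | Route that can end it |
|---|---|---|
| Important deviation | 7.5.1 item 6, then 7.5: visits to Week 8 | 4.4.3: trial withdrawal considered |
| Drug-related or other adverse event | 7.5.1 item 3, read as stopping IP, then 7.5 | 6.5.1: trial ended for that participant; 7.5.1 item 3, read as ending participation |

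The sections do not say which route governs.

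**2. Safety observation that can be lost**

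For a completer, the last visit is at Day 56 (±3 days), so recording runs to about Day 56. For a participant who leaves in the first days, the longer of the early last visit and 28 days post-dose is Day 28. The possible loss is 56 − 28 = 28 days of adverse-event recording, plus scheduled laboratory tests, ECG and visits after the early End of Trial visit. Section 4.2.2 gives a median of 56 days to the last detectable concentration after a single 600 mg dose, so drug can still be present in the unobserved period.

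**3. Effect on the primary analysis**

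Sensitivity Analysis 1 (13.4.5.1) imputes failure for participants who discontinue before a documented failure. That treats their outcome as missing, so under the observed-data rule of 13.4.5 they do not contribute to the primary comparison.

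*The plan's own figure (13.2).* 160 × 0.95 = 152 evaluable, or 76 per arm. With 45% against 22.5% and two-sided alpha 0.05, the pooled normal approximation gives:

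power = Φ{[0.225√76 − 1.96√(2 × 0.3375 × 0.6625)] / √(0.45 × 0.55 + 0.225 × 0.775)} = Φ(1.00) = 84.2%.

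Exact Fisher power is 80.0%. The stated power of at least 80% is reproduced, and the sample size is not in dispute.

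*Deleting one participant from an arm of 76 at the planning rates*

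- Placebo, 34.2/76 = 45.0%. Deleting a failure gives 33.2/75 = 44.3% (−0.7 points). Deleting a non-failure gives 34.2/75 = 45.6% (+0.6).
- Rademikibart, 17.1/76 = 22.5%. Deleting a failure gives 16.1/75 = 21.5% (−1.0). Deleting a non-failure gives 17.1/75 = 22.8% (+0.3).

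*Power.* If total loss were 10% instead of 5% (an assumption), 72 per arm would remain and pooled power would be 82.2%. Power is not the main issue.

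*Direction of bias (illustration only; the fractions are assumed).* If a fraction q of would-be failures left one arm undocumented, its observed rate would be p(1 − q)/(1 − pq).

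- Placebo only, q = 10% to 30%: the rate is 42.4% to 36.4%, and the difference falls from 22.5 to between 19.9 and 13.9 points.
- Rademikibart only, same q: the rate is 20.7% to 16.9%, and the difference rises to between 24.3 and 28.1 points.

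The direction depends on which arm loses participants, which the protocol cannot tell us.

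**The case against.** The strongest reply is that this is loose wording and not a rule that removes people. Section 4.4.3 requires a discussion and does not favour withdrawal. Section 7.6 sets retention as the default. In Section 6.5.1 the operative instruction is that dosing stops, and the reference to ending the trial only describes the event. All of this stands. A reader might infer that the protocol orders removal after a deviation or a drug-related event; it does not.

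A reader might also infer that worsening participants would be the ones removed, because prohibited treatment often follows worsening. The endpoint in Section 10.1 largely answers that. An emergency or unscheduled visit for worsening, or the need to intensify drug treatment, is itself a failure, so the outcome will usually be recorded before any discussion of a deviation. Table 3 also makes exceptions for some treatment of exacerbations. The concern therefore rests on wrong dose, ineligible enrolment and drug-related events.

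The safety loss is partial. Adverse events are recorded to at least 28 days post-dose, documented events are followed (11.8), and possibly related serious events that come to light after participation ends are still reported (11.6). The early End of Trial visit includes laboratory tests and ECG. A reader might infer that immunogenicity data are lost as well, but Section 12.3 takes a serum sample at the final visit of withdrawn participants.

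Finally, Section 13.4.5.1 plans a failure-imputation analysis and a tipping-point analysis. These show how far missing outcomes could matter; they do not recover them.

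**Conclusion.** The point holds as an internal inconsistency with a real but unquantified consequence. The protocol mixes discontinuation of IP with withdrawal from the trial, and after a single dose the second serves no exposure purpose. What can be lost is scheduled follow-up after one early visit, up to 28 days of adverse-event recording, and the primary outcome of anyone removed before Day 28 without a documented failure. Removals after a failure, or after Day 28, cost no primary data.

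The loss is possible, not certain. The document gives no rate of investigator- or sponsor-initiated withdrawal, so the total effect cannot be derived; the bias figures above rest wholly on assumed fractions. A reader might equate one lost participant with one seventy-sixth of an arm's failure rate. That is the effect of reversing a known outcome, and deletion has the smaller effect of about 0.3 to 1.0 points. A claim that the trial will lose its primary data or its power is not supported.

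**What to change.** Reconcile Sections 4.4.3, 6.5.1, 7.5, 7.5.1 and 7.6 so that stopping IP and ending data collection are separate decisions with separate wording.

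- For participants already dosed, state that an important deviation is not by itself a reason to end follow-up. Record it and handle it through the Per-Protocol Set, which Sections 13.3 and 13.4.5.2 already provide. Collect outcome and safety data to Week 8 where the participant agrees.
- For adverse events, have the sponsor settle how 6.5.1 and 7.5.1 item 3 relate to 7.5. This review does not say which stopping passage should prevail.
- Keep the existing routes out of the trial: withdrawal of consent, consent that was never validly obtained (itself an important deviation in 4.4.3), and the Investigator's judgement of the participant's best interest. A rule allowing only consent withdrawal, death or loss to follow-up would be too absolute.

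The cost is wording in a protocol amendment and a few more scheduled visits for participants who would otherwise have left. No new procedure is needed, and dose and sample size are unchanged.
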